5.6 Test Drug Concentration

Not applicable to this study.

5.7 Other Measurements, Assessments or Methods

Not applicable to this study.

5.8 Total Amount of Blood Drawn

Table 3 shows the specifics of blood sample collection, including the category/type of test, time points for blood collection, and the volume of blood samples. The total volume of blood to be drawn from each subject is 25 mL.

Table 3 Blood Sample Collection During the Study

Test	Time Point	Volume of Blood per Collection	Scheduled Number of Collections	Total Volume	Total Volume of Blood Per Subject
Serum Chemistry	Visit 1	4 mL	3	12 mL	25 mL
	Visit 2				
	Visit 5				
Hematology	Visit 1	2 mL	3	6 mL	
	Visit 2				
	Visit 5				
Coagulation	Visit 1	3 mL	1	3 mL	
Serum PSA	Visit 1	4 mL	1	4 mL	

PSA = prostate-specific antigen

6 DISCONTINUATION

6.1 Discontinuation of Individual Subject(s)

A discontinuation is a subject enrolled in the study for whom study treatment is prematurely discontinued, for any reason.

The subject is free to withdraw from study treatment and/or the study for any reason and at any time without giving reason for doing so and without penalty or prejudice. The Investigator is also free to terminate a subject's involvement in the study at any time if the subject's clinical condition warrants it.

If a subject is discontinued from the study and has an ongoing AE or an unresolved laboratory result that is significantly outside of the reference range, the Investigator will attempt to provide follow-up until the condition stabilizes or is no longer clinically significant.

Treatment Discontinuation Criteria for Individual Subjects:

- Due to an AE
 - When continuation in the study is judged to be difficult due to development of an AE or SAE
 - When continuation in the study is judged to be difficult due to aggravation of a concurrent disease requiring a change in treatment from the protocol
- Lack of efficacy
- Withdrawn consent
- Lost to follow-up
- Deviation from the inclusion or exclusion criteria during the Screening period
- Protocol deviations
 - When a subject is found not to have met the inclusion criteria at enrollment, or to have met the exclusion criteria after enrollment and therefore, was determined to be ineligible for the study
 - Any other serious violation of the protocol
- Other
 - When the Investigator judges that the subject must be withdrawn from the study, for any reason.

For those subjects who are withdrawn from the study after study drug administration, the examinations and evaluations scheduled for the final visit of the treatment period will be performed at the time of discontinuation, as much as possible (See Section V, Figure 1 Study Design Flow Chart and Table 1 Schedule of Assessments). If the subject is discontinued due to an AE, appropriate treatment will be provided, as necessary.

The Investigator will record the date and reason for the subject discontinuation and enter in the eCRF.

6.2 Discontinuation of the Site

If an investigator intends to discontinue participation in the study, the Investigator must immediately inform the Sponsor and the Head of the study site.

6.3 Discontinuation of the Study

The Sponsor may terminate this study prematurely, either in its entirety or at any study site, for reasonable cause provided that written notice is submitted in advance of the intended termination. Advance notice is not required if the study is stopped due to safety

concerns. If the Sponsor terminates the study for safety reasons, the Sponsor will immediately notify the Investigator and subsequently provide written instructions for study termination.

7 STATISTICAL METHODOLOGY

The statistical analysis will be coordinated by the responsible biostatistician of API. A Statistical Analysis Plan (SAP) will be written to provide details of the analysis, along with specifications for tables, listings, and figures to be produced. The SAP will be finalized before breaking the treatment code. Any changes from the planned analyses in the SAP will be described and justified in the Clinical Study Report.

7.1 Sample Size

The sample size for this study was based on 248 subjects per treatment group (using the Full Analysis Set [FAS]) to provide 90% power to detect a 0.7 reduction in the mean number of micturitions/24 hours in the mirabegron group compared to the placebo group, at a two-sided alpha level of 0.05. A standard deviation (SD) of 2.4 is assumed. Assumptions for the mean reduction and SD are based on data from previous studies (178-CL-048, 178-CL-090 and 905-JC-001; Table 4-6). If 90% of the randomized subjects are evaluable for efficacy, 550 subjects should be randomized, with 275 subjects randomized to each treatment group.

Table 4 178-CL-048¹⁷ Change from Baseline in the Mean Number of Micturitions at the Final Assessment

	Placebo (n = 368)	Mirabegron 50 mg (n = 369)
Baseline	11.29 ± 2.748	11.15 ± 2.650
Final assessment	10.44 ± 2.777	9.48 ± 2.528
Change	-0.86 ± 2.354	-1.67 ± 2.212

*Mean ± SD

Table 5 178-CL-090²¹ Change from Baseline to Last Visit in Mean Number of Micturitions Per 24-hour

	Placebo				Mirabegron 50mg			
	N	mean	SE	95% CI	N	mean	SE	95% CI
Overall	323	-1.48	0.178	(-1.83, -1.13)	338	-2.04	0.174	(-2.38, -1.70)
China								
India								
Korea								
Taiwan								

* Adjusted change from baseline results are generated from the ANCOVA model with treatment group as a fixed factor and baseline as a covariate.

Table 6 905-JC-001⁷ Changes in average 24-hour frequency of urination

	Tamsulosin 0.2mg + Placebo (n = 209)	Tamsulosin 0.2mg + Vesicare 5.0mg (n = 208)
Adjusted mean (95% confidence interval)	-0.22 (-0.51, 0.06)	-1.06 (-1.34, -0.77)

*Analysis of covariance was performed with the treatment group as a factor and baseline average 24-hour frequency of urgency as a covariate, and multiplicity was adjusted by a closed testing procedure to start with comparison of the Ha0.2mg+Vc5.0mg group.

7.2 Analysis Set

The analysis will be performed using the following analysis populations, based on ICH guidelines E3 and E9. The final handling of the analysis sets will be decided with the decisions based on the opinions and advice of medical experts prior to breaking of the randomization code.

7.2.1 Full Analysis Set

The primary analysis dataset is the FAS, which will consist of all subjects who are randomized and receive at least 1 dose of double-blind study drug and have a Baseline micturition measurement and at least 1 post-Baseline micturition measurement.

All secondary efficacy analyses will be performed on the FAS.

7.2.2 Per Protocol Set

Subjects from the FAS who meet all of the following criteria will be included in the Per Protocol Set (PPS):

1. Those subjects who did not violate the inclusion criteria.
2. Those subjects who did not violate the exclusion criteria.
3. Those subjects with drug compliance during the Screening period and Treatment period of not less than 80%.
4. Those subjects who took the study drug during the Treatment period for 42 days or longer from the day following dispensing. However, subjects who discontinued the study for efficacy-related reasons, such as insufficient therapeutic effect, will be included in the PPS, even if the drug was taken for less than 42 days.
5. Subjects with diary entries for at least 2 of the 3 consecutive days at Visit 2 and the last visit during the Treatment period.
6. Subjects who did not receive any of the prohibited concomitant medications/therapies that may affect the evaluation of efficacy.

7.2.3 Safety Analysis Set

The analysis of safety data will be performed on the Safety Analysis Set (SAF), which will include all subjects who received at least 1 dose of double-blind study medication.

7.3 Demographics and Other Baseline Characteristics

Demographics and other baseline characteristics will be summarized by treatment group for the FAS, PPS, and SAF. Descriptive statistics will include: number of subjects; mean,

SD, minimum, Q1, median, Q3 and maximum for continuous endpoints; and frequency and percentage for categorical endpoints.

7.4 Analysis of Efficacy

The efficacy analysis will be conducted on the FAS, with the PPS as a supportive analysis.

7.4.1 Analysis of Primary Endpoint

7.4.1.1 Primary Analysis

The primary efficacy endpoint, change from Baseline to End of Treatment in the mean number of micturitions per 24 hours, will be analyzed using an Analysis of Covariance (ANCOVA), including treatment group and region as fixed factors and baseline as a covariate. Within the framework of the ANCOVA model, point estimates and two-sided 95% confidence intervals for the mean change from Baseline both within and between treatment groups will be calculated. The two-sided significance level will be set at 5%.

The hypotheses for the treatment group comparisons are as follows:

H_0 : The change from Baseline to End of Treatment in the mean number of micturitions over 24 hours is the same in subjects who received mirabegron compared to those who received placebo.

H_1 : The change from Baseline to End of Treatment in the mean number of micturitions over 24 hours is not the same in subjects who received mirabegron compared to those who received placebo.

The primary and secondary efficacy analyses will be conducted using the FAS, which includes all subjects who receive at least 1 dose of double-blind study medication *and* have both a Baseline and post-Baseline micturition assessment.

For those subjects who discontinue the study prematurely, the End-of-Treatment assessment will be analyzed. The End-of-Treatment assessment is defined as the last post-Baseline assessment during the double-blind study period for which primary efficacy data are available.

Continuous variables will be summarized using descriptive statistics, including mean, standard deviation, minimum, Q1, median, Q3 and maximum. Categorical variables will be described using absolute and relative frequency.

7.4.1.2 Secondary Analysis

The primary efficacy endpoint, change from Baseline to End of Treatment in the mean number of micturition episodes per 24 hours, will be analyzed using a Mixed Model Repeated Measure (MMRM) for the secondary analysis. Further details on the MMRM analyses will be provided in the Statistical Analysis Plan (SAP).

7.4.1.3 Subgroup Analysis

Subgroup analyses will include analyses by geographic region and by urgency incontinence at Baseline. Further details on subgroup analyses will be provided in the SAP.

7.4.2 Analysis of Secondary Endpoints

The secondary endpoints include the change from Baseline to End of Treatment in:

- Mean number of urgency episodes/24 hours
- Mean number of urgency incontinence episodes/24 hours
- Mean number of incontinence episodes/24 hours
- Mean number of nocturnal episodes
- Mean volume voided per micturition
- Total OABSS score
- Subscale score from OABSS score
- Total IPSS score
- Subscale score from IPSS score
- Symptom Bother and total Health-Related QoL scores, as assessed by the OAB-q questionnaire.

The secondary endpoints will be analyzed using the FAS, with the PPS as a supportive analysis. For the changes in mean number of incontinence and urge incontinence episodes, the analysis will be based on those subjects who have at least 1 incontinence episode at Baseline.

For the change in the mean number of nocturia episodes, the analysis will be based on those subjects who had at least 1 nocturia episode at Baseline.

The secondary efficacy endpoints, except for the changes in mean number of incontinence and urge incontinence episodes, will be analyzed using an Analysis of Covariance (ANCOVA), including treatment group and region as fixed factors and baseline as a covariate. Within the framework of the ANCOVA model, point estimates and two-sided 95% confidence intervals for the mean change from Baseline both within and between treatment groups will be calculated. The two-sided significance level will be set at 5%.

The changes in mean number of incontinence and urge incontinence episodes will be analyzed using a Stratified Rank Analysis of Covariance (RANCOVA). Details on the RANCOVA analyses will be provided in the Statistical Analysis Plan (SAP).

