Variable	Any quantity that varies; any attribute, phenomenon, or event that can have different qualitative or quantitative values.

IV. SYNOPSIS

Date and Version # of Protocol Synopsis:										
Sponsor: Astellas Pharma Inc. (API)		Protocol Number: 178-MA-3016								
Name of Study Drug: Mirabegron		Phase of Development: 4								
Title of Study: A Phase 4, Double-Blind, Randomized, Placebo-controlled Multicenter Study to Evaluate the Efficacy, Safety, and Tolerability of Mirabegron in Male Subjects with OAB Symptoms, while taking the Alpha Blocker, Tamsulosin, for BPH										
Planned Study Period: December 2015 to August 2017										

Study Objective(s):
 
Primary Objective: To study the efficacy of mirabegron versus placebo in male patients with overactive bladder (OAB) symptoms while taking the alpha blocker, tamsulosin, for benign prostatic hypertrophy (BPH)
 
Secondary Objective: To assess the safety and tolerability of mirabegron versus placebo in male patients with OAB symptoms while taking the alpha blocker, tamsulosin, for BPH
 
Other Objectives: To assess patient-reported outcomes as measured by Symptom Bother, and Total Health-Related Quality of Life scores as assessed by the Overactive Bladder questionnaire (OAB-q) and IPSS (QoL) of mirabegron versus placebo in male subjects with OAB symptoms who are taking the alpha blocker, tamsulosin, for BPH.
 
The hypothesis being tested is that mirabegron is superior to placebo in the treatment of OAB symptoms.
										
Planned Total Number of Study Centers and Location(s): Approximately 55 centers (Japan: ~50 centers; Korea: ~5 centers)										
Study Population: Men ≥40 years of age with OAB symptoms and taking the alpha blocker, tamsulosin, for BPH										
Number of Subjects to be Enrolled/Randomized: A total of 550 subjects (490 in Japan; 60 in Korea), with 275 subjects randomized (1:1) to each treatment group.										

Study Design Overview
 
This is a randomized, double-blind, placebo-controlled, parallel group, multi-center study that will compare mirabegron with placebo in the treatment of OAB symptoms in men who are taking tamsulosin for BPH.
 
If a drug for the treatment of BPH (e.g., PDE5 inhibitor or alpha 1 blocker other than tamsulosin) is to be changed to tamsulosin to enroll a subject in this clinical study, the change to tamsulosin should be done only after ICF signature.
										

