Night time is the period between after sleep onset time and the wake-up time the following day (micturitions at the same time as the wake-up time will be excluded). The diary must be completed for at least 2 consecutive days to allow assessment of night time frequency for at least 1 night. Any data collected before the wake-up time on the first day of diary completion and after the sleep onset time on the third day cannot be included in the assessment of night time frequency. Only those subjects whose symptoms were confirmed at baseline (Visit 2) will be analyzed.
If there is no nocturia episode on all evaluable night time in each visit, then the mean number of nocturia episodes/24 hours is equal to zero. Therefore if the mean number of nocturia episodes per 24 hours is “0” at baseline, this subject is excluded from the analysis.

- Mean volume voided per micturition
Calculation is similar to ‘micturition’, but sum urinary volumes where the volume voided is > 0 and where ‘Urinary incontinence’ is not indicated, rather than count the episodes. The denominator will be the number of micturitions where the volume voided is > 0 and where ‘urinary incontinence’ is not indicated. Only those subjects whose symptoms were confirmed at baseline (Visit 2) will be analysed.

- Total OABSS score
For each patient, OABSS total score will be the sum total of the score of each item (Questions 1-4).
- Subscale scores (daytime frequency, nighttime frequency, urgency and urgency incontinence) from OABSS score
For each patient, OABSS subscale scores will be the score of each item (Questions 1-4).
- Total IPSS score
For each patient, total IPSS score will be the sum total of the score of each item (Questions 1-7).
- Subscale scores (storage subscale, voiding subscale-1, voiding subscale-2 and quality of life item) and individual scores from IPSS score
For each patient, IPSS subscale scores will be calculated by following each formula. Storage subscale is derived as sum of scores for questions 2, 4, and 7. Voiding subscale-1 is derived as sum of scores for questions 3, 5, and 6. Voiding subscale-2 is derived as sum of voiding subscale-1 and the score for question 1.
For each patient, Individual scores and IPSS QoL score will be the score of each item (Questions 1-7 and quality of life item).

- Symptom Bother and Total Health-Related Quality of Life scores (Total HRQL scores), as assessed by OAB-q

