7 STATISTICAL METHODOLOGY

7.1 General Considerations

Assessment at Visit 2 (Day 1) will be treated as baseline for efficacy and safety analysis.

The End of Treatment assessment is defined as the last post-Baseline assessment during the double-blind study period for which the primary efficacy data are available.

For continuous variables, descriptive statistics will include the number of subjects (n), mean, standard deviation, minimum, Q1 (25th percentile), median, Q3 (75th percentile) and maximum. Frequencies and percentages will be displayed for categorical data. Percentages by categories will be based on the number of subjects with no missing data, i.e. will add up to 100%.

Summaries based on FAS and PPS (e.g. disposition, baseline and efficacy data) will be presented by planned treatment group, unless specifically stated otherwise. Safety analysis and other summaries based on SAF will be presented by actual treatment received.

All statistical comparisons will be made using two sided tests at the $\alpha=0.05$ significance level unless specifically stated otherwise. All null hypotheses will be of no treatment difference, all alternative hypotheses will be two-sided, unless specifically stated otherwise.

All data processing, summarization, and analyses will be performed using Windows SAS[®] Version 9.4. Specifications for table, figures, and data listing formats can be found in the Tables, Listings and Figures (TLF) specifications for this study.

For the definition of subgroups of interest please refer to section [7.8](#)

Total and subscale score of OABSS, IPSS and OAB-q are as follows:

Name of score	Subscale score	Calculation	Range
IPSS (Question 1-7 and Quality Life Item)	Storage Subscale	Sum of Question 2,4 and 7	0-15
	Voiding Subscale-1	Sum of Question 3, 5 and 6	0-15
	Voiding Subscale-2	Sum of Question 1, 3, 5 and 6	0-20
	Quality of Life Item	-	0-6
	Total Index Score	Sum of Question 1 to 7	0-35
OABSS (Question 1-4)	Daytime frequency	Question 1	0-2
	Nighttime frequency	Question 2	0-3
	Urgency	Question 3	0-5
	Urgency incontinence	Question 4	0-5
	Total Score	Sum of Question 1 to 4	0-15
OAB-q (Question 1-33)	Symptom bother	Sum of Q1-8	0-100
	Coping	Sum of Q9,11,16,21,22,26,32,33	0-100
	Concern	Sum of Q12,13,14,19,23,25,29	0-100
	Sleep	Sum of Q10,15,17,24,30	0-100
	Social Interaction	Sum of Q18,20,27,28,31	0-100
	Total Health-Related Quality of Life scores	Sum of OAB-q subscale scores (Coping, Concern, Sleep, Social Interaction)t	0-100

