7.4.2 Analysis of Secondary Endpoints

The secondary endpoints are actual value and the change from Baseline to post-baseline and End of Treatment in:

- Mean number of micturations/24 hours (except for End of Treatment visit)
- Mean number of urgency episodes/24 hours
- Mean number of urgency incontinence episodes/24 hours
- Mean number of incontinence episodes/24 hours
- Mean number of nocturia episodes
- Mean volume voided per micturition
- Total OABSS score
- Subscale scores (daytime frequency, nighttime frequency, urgency and urgency incontinence) from OABSS score
- Total IPSS score
- Subscale scores (storage subscale, voiding subscale and quality of life item) and individual scores from IPSS score
- Symptom Bother and total Health-Related QoL scores, as assessed by the OAB-q questionnaire.

For the changes in mean number of incontinence and urge incontinence episodes, the analysis will be based on those subjects who have at least 1 incontinence episode at Baseline.

For the change in the mean number of nocturia episodes, the analysis will be based on those subjects who had at least 1 nocturia episode at Baseline.

Concerning actual value and the change from baseline to post-baseline of the secondary endpoints, descriptive statistics will be calculated by treatment group at each visit and at the End of Treatment for FAS and PPS.

Mean (+/- SD) plot for actual value and change from baseline to post-baseline will be presented by treatment group for FAS. In addition, for mean number of micturations/24 hours, this plot will be presented by subgroups defined in section 7.4.4 for FAS.

Radar charts of the mean of actual value for OABSS and IPSS will be made to present relationship between each question by treatment group for FAS.

For individual score from OABSS score and IPSS score, frequency tabulations of scores will be presented for each treatment group at each visit and at the End of Treatment for FAS and PPS.

Except for the changes in mean number of micturations, incontinence and urge incontinence episodes, change from Baseline to End of Treatment of these endpoints will be analyzed using an ANCOVA (refer to section 7.4.1.1 for detail) for FAS and PPS.

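### The secondary efficacy tests (23–24 under the SAP) are each held to two-sided 5% with no order, gate or nominal label, so family-wise error across them is uncontrolled

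*Protocol*

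**What the plan says.** The primary inference is a single test. Protocol 7.4.1.1 and SAP 7.4.1.1 specify one ANCOVA on the Full Analysis Set (FAS) of the change to End of Treatment in micturitions per 24 hours. The sample size in Protocol 7.1 rests on that endpoint alone, "at a two-sided alpha level of 0.05".

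For the secondary endpoints, Protocol 7.4.2 prescribes the same ANCOVA and the same rule: "The two-sided significance level will be set at 5" percent. SAP 7.1 is broader: "All statistical comparisons will be made using two sided tests at the" 0.05 level, unless otherwise specified. That also covers the rank ANCOVA of the two incontinence endpoints. SAP 7.4.2 has no significance level of its own and refers back to 7.4.1.1 for the ANCOVA.

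Protocol 7.4.2 lists ten bullets without naming the subscales. SAP 6.1.2 names them and adds the individual IPSS scores. It also defines two nested voiding scores: "Voiding subscale-2 is derived as sum of voiding subscale-1 and the score for question 1". The corresponding line of SAP 7.4.2 mentions voiding only once: "Subscale scores (storage subscale, voiding subscale and quality of life item) and individual scores from IPSS score".

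Neither document contains a testing order, a condition on the primary result, an alpha adjustment, or a statement that secondary p-values are nominal. The only multiplicity wording is the footnote to Table 6 in Protocol 7.1, which describes an earlier trial.

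**The concern.** The secondary tests get the same decision rule as the one confirmatory test. They cannot be taken as implicitly descriptive, because the plan has a separate exploratory tier below them. For that tier SAP 7.4.3 specifies only summaries, Kaplan-Meier estimates and confidence intervals, with no between-group test.

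Followed as written, the plan lets each secondary result be called significant at 5%, whatever happens to the primary and however many are examined. The Protocol synopsis and SAP 3.1 word the overall aim more broadly than the primary endpoint: "The hypothesis being tested is that mirabegron is superior to placebo in the treatment of OAB symptoms". If the primary missed, no rule would say how a significant urgency, nocturia or OABSS result should be treated. If the primary succeeded, no rule would say which secondary claims are supported.

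**Working it through.** **Step 1. The plan's own figure.** Inputs from Protocol 7.1: difference 0.7, SD 2.4, two-sided alpha 0.05, power 90%.

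n per group = 2 × (1.960 + 1.282)² × 2.4² / 0.7², which is just over 247 and rounds up to 248, as stated. Power at 248 per group is 90.1% by the normal approximation and 90.0% by the t-test. This calculation uses the 5% once, on one endpoint. The documents state no family-wise rate for the secondary endpoints, so there is none to reproduce.

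**Step 2. Count the tests** (End of Treatment, FAS; SAP 6.1.2 and 7.4.2).

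| Group | Tests |
|---|---|
| Diary: urgency, urgency incontinence, incontinence, nocturia, volume voided | 5 |
| OABSS: total and 4 items | 5 |
| IPSS: total, storage, voiding-1, voiding-2, quality of life, 7 individual items | 12 |
| OAB-q: Symptom Bother, Total HRQL | 2 |
| Total | 24 |

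Counting voiding once, as SAP 7.4.2 writes it, gives 23. Leaving out the seven individual IPSS items, which the Protocol does not list, gives 17 or 16. The repeats on the Per Protocol Set are not counted.

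**Step 3. Independent tests, no effect on any endpoint.**

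- At least one p<0.05 in either direction: 1 − 0.95^k. For k = 24 this is 1 − 0.95^24 = 70.8%; for k = 17, 58.2%.
- At least one significant result favouring mirabegron: 1 − 0.975^k. For k = 24 this is 45.5%; for k = 17, 35.0%.
- Expected false positives for k = 24, at any correlation: 24 × 0.05 = 1.2, of which 24 × 0.025 = 0.6 favour mirabegron.

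**Step 4. Correlated tests.** The endpoints overlap by construction, so independence is only an upper bound. The documents give no correlations. A common correlation r was therefore assumed between test statistics, with each endpoint signed so that improvement is positive: Z_i = √r·W + √(1−r)·E_i, where W and the E_i are independent standard normal. A test counts as significant when |Z_i| > 1.96, and as favouring mirabegron when Z_i > 1.96. Results are from 400,000 simulated draws; the r = 0 row is from Step 3.

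| r | 24 tests, either direction | 24 tests, favouring mirabegron | 17 tests, either direction | 17 tests, favouring mirabegron |
|---|---|---|---|---|
| 0 | 70.8% | 45.5% | 58.2% | 35.0% |
| 0.3 | 59.5% | 31.2% | 49.4% | 25.4% |
| 0.5 | 45.8% | 22.9% | 38.6% | 19.4% |
| 0.7 | 31.0% | 15.5% | 26.9% | 13.5% |
| 0.9 | 16.3% | 8.2% | 14.8% | 7.4% |

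Counting voiding once changes little: at r = 0.5, 23 tests give 44.8% and 22.6%, and 16 tests give 37.6% and 18.8%. The reference for a single test is 5% in either direction and 2.5% favouring mirabegron.

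**The case against.** The strongest reply is that the confirmatory inference is intact. The formal hypotheses in Protocol 7.4.1.1 and SAP 7.4.1.1 concern micturitions only, none is written for a secondary endpoint, and no passage says that a secondary result can establish efficacy. This stands. A reader might infer that the plan lets a secondary result rescue a failed primary. The documents do not say so; they only fail to rule it out.

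A reader might also infer that a spurious positive finding on OAB symptoms is likely. The figures do not support that:

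- The either-direction chance with 24 tests exceeds one half only when correlation is low. It is 53.0% at 0.4 and 45.8% at 0.5.
- Low correlation throughout is implausible. The OABSS and IPSS totals contain items that are tested separately, one voiding score contains the other, and urgency incontinence is a subset of incontinence.
- For a false result favouring mirabegron the chance stays below one half even under independence.
- Several of the scores measure voiding or emptying, so not every false positive would be an OAB finding.

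Setting the family-wise rate against 5% as a multiple of the stated alpha would also mislead. The documents state 5% per comparison and promise no family-wise rate for these endpoints. The Per Protocol repeats are expressly supportive and do not add to the concern.

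The core point remains. A per-test significance rule is written down for the secondaries, and nothing limits the claims that may follow from it.

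**Conclusion.** The point holds as a gap in the control and labelling of secondary inference. It does not affect the primary result.

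With 24 tests, the chance of at least one false secondary result favouring mirabegron is about 23% at a correlation of 0.5, and ranges from 8% at 0.9 to 46% under independence. Dropping the seven IPSS items lowers this to 19%, with a range of 7% to 35%. Every value tried is well above the 2.5% of a single test.

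These figures assume no effect on any secondary endpoint and one common correlation. Actual correlations will differ between pairs, so the figures give an order of magnitude. The absence of an order, a gate or a nominal label does not depend on these assumptions.

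**What to change.** In Protocol 7.4.2, replace the 5% sentence with the wording below. Add the same wording to SAP 7.1, as an exception to its general 0.05 rule, and to SAP 7.4.2:

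> The only confirmatory test is the FAS ANCOVA of the primary endpoint; p-values for secondary endpoints are nominal and no confirmatory claim will be based on them.

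If the sponsor wants confirmatory secondary claims, it should choose its own short fixed sequence before unblinding. The sequence would be tested only after the primary is significant, each step at two-sided 5%, stopping at the first failure. That holds the error rate across the sequence at 5% or less. The remaining secondary p-values would stay nominal.

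Neither option changes the sample size, the data collected or the primary analysis. The cost is that secondary results outside such a sequence can no longer be presented as statistically significant proof of effect. The Protocol change must also be documented as an amendment or revision under Protocol 8.3.3, which may require ethics committee and competent authority approval or notification.
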